Procedures for effectiveness trial. After Aim 1 is complete, program-wide implementation of MBC will begin. The initial training will consist of a series of workshop style trainings conducted during regular agency staff meetings and ongoing consultation will be provided to agency staff thereafter. The training approach is a data-driven one, where questionnaires are used throughout the training and consultation to tailor implementation to that specific context. These questionnaires will be considered part of the implementation activities and will be administered to all staff members participating in the trainings. Clinicians who consent to be in the research study will be giving permission for these implementation data to be linked to the research data they provide for their clients; responses from other HCA staff will be de-identified and used to characterize the implementation under Aim 3. Prior to extracting these data for research purposes, we will submit a variable list to the IRB for approval. When the initial training is complete, the trial will begin program-wide at the participating HCA clinics. As the clinics add clients ages 11-17 to the Mirah system, the system will automatically randomize them to either unidimensional or multidimensional MBC on a 1:1 ratio. All clients and their caregivers will complete MBC measures as part of routine services, and the researchers will receive limited identifier datasets containing MBC data and Mirah metadata for all participants, an identifiable

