Sample size and power calculations. Given the preliminary nature of this pilot study, power calculations focused on power for the analyses of the group differences in outcomes (Hypothesis 2c.1). Power calculations were conducted using Optimal Design 3.1. We assumed 8% of the outcome variance at the clinician level¹³⁵ for an n of 22 clinicians (over the duration of the study) and 900 adolescents, $\beta = .80$, and $p = .05$. Using these estimates, Aim 2c, examining the impact of feedback condition on treatment response (assessed by the SFSS) will be optimally powered to detect a small effect of $d = .25$. The only previous estimate of differences between multidimensional and unidimensional MBC focused on the NOT subgroup only, finding an effect of ($d = .31$); the overall effect size for this study is expected to be smaller because the analyses will focus on the NOT and OT groups combined. Using a more conservative small effect size of $d = .20$ yields power of approximately .75. With respect to power assessing differences by feedback condition in the Research Subsample (n = at least 22 clinicians and 400 adolescents) will be optimally powered for a small-moderate effect of $d = .30$. Assuming an effect size of $d = .25$ yields power of .62.

DATA SECURITY, STORAGE, AND QUALITY CONTROL

Quantitative data will be collected electronically via either the University of Miami REDCAP system or directly through Mirah. Mirah is a HIPAA compliant system for collecting and scoring clinical measures. It uses Secure Sockets Layer (SSL) encryption to protect all data during transfers and stores is on a secure server. Data access will be restricted to study personnel, with permissions set to only those necessary to perform

tasks. Whenever possible, staff will download data directly from REDCAP or Mirah, but any file transfers between sites will be done via an approved secure platform such as secure send. Downloaded files will be stored on the psychology department's server, box.com, one drive, and/or google drive. The project coordinator will be regularly reviewing data for threats to data quality, such as missing data. Built-in validation protocols in REDCAP and Mirah will prevent entry of invalid responses.

Qualitative interview recordings, transcripts, and codes will also be stored securely on psychology department's server, box.com, one drive, and/or google drive.

13) Provisions to Monitor the Data to Ensure the Safety of Subjects*

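### The two power statements for N = 900 cannot both hold if 'optimally powered' at d = .25 means the plan's .80 target, because power of about .75 at d = .20 then does not follow

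*Combined protocol and SAP*

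**What the plan says.** All the figures stand in section 12 (Data Management), under Sample size and power calculations.

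- **Software and design.** "Power calculations were conducted using Optimal Design 3.1". The inputs are 8% of outcome variance at the clinician level "for an n of 22 clinicians (over the duration of the study) and 900 adolescents", a target printed as β = .80 (evidently power of .80), and p = .05.
- **Full sample.** Aim 2c on the SFSS "will be optimally powered to detect a small effect of $d = .25". Then: "Using a more conservative small effect size of $d = .20$ yields power of approximately .75".
- **Expected effect.** The one earlier estimate, d = .31, came from the not-on-track subgroup only, and "the overall effect size for this study is expected to be smaller".
- **Research Subsample** (400 adolescents, at least 22 clinicians). The comparison "will be optimally powered for a small-moderate effect of $d = .30". Then: "Assuming an effect size of $d = .25$ yields power of .62".

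Section 10 (Procedures for effectiveness trial) makes the client the unit of allocation: "the system will automatically randomize them to either unidimensional or multidimensional MBC on a 1:1 ratio". The Aim 2c analysis nests clients within treating clinician and adjusts for clinic. The term 'optimally powered' is not defined anywhere.

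**The concern.** For one design, power depends on the effect size divided by a single standard error, so one pair of effect size and power fixes the power at every other effect size. The two N = 900 statements come from the same stated design. If the first is a statement about .80 power, they imply different standard errors.

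This is the power statement for the main comparison, on a primary endpoint. The plan expects an overall effect below .31, so d = .20 to .25 is the range that matters. A reader of a null result cannot tell whether power at d = .20 was .75 or .61, or whether the 80% detectable effect was .21 or .25.

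**Working it through.** **Inputs from section 12.** 22 clinicians; N = 900 (900/22 = 40.9 per clinician); n = 400 (400/22 = 18.2 per clinician); alpha .05; target power .80. Sidedness is not stated; two-sided is assumed, with a one-sided check below.

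**1. Trying to reproduce the printed figures.** Take clients randomised 1:1 within J = 22 clinicians, with effect variance s across clinicians and residual variance c:

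SE² = (s + 4cJ/N)/J.

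With s = 0 and c = 1, SE = √(4/900) = .0667. With c = .92 (8% removed at clinician level), SE = √(3.68/900) = .0639. Using either a normal reference or t with 21 df:

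| N = 900 | Computed, s = 0 | Plan |
|---|---|---|
| Power at d = .20 | .82 to .88 | about .75 |
| Power at d = .25 | .95 to .97 | 'optimally powered' |
| 80% detectable d | .18 to .20 | .25, if the phrase means .80 |

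So neither N = 900 figure follows from the stated inputs alone. Some unstated input was used.

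**2. Check that needs no variance model.** Let λ = d/SE. Two-sided power is approximately Φ(λ − 1.960), and λ is proportional to d.

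- *Taking .80 at d = .25.* λ = 1.960 + .842 = 2.802, so SE = .25/2.802 = .089. At d = .20, λ = 2.802 × .20/.25 = 2.241, and power is Φ(.281) = **.61**, against the printed .75.
- *Taking .75 at d = .20.* λ = 1.960 + .674 = 2.634, so SE = .20/2.634 = .076. At d = .25, λ = 2.634 × .25/.20 = 3.293, and power is Φ(1.333) = **.91**. The 80% detectable effect is .20 × 2.802/2.634 = **.213**.

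The gap is 14 points at d = .20 or 11 points at d = .25. It survives the obvious variations:

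- *t with 21 df:* .61 and .91 again.
- *One-sided alpha:* .635 and .895, detectable effect .214.
- *'Approximately .75' read as .70 to .78:* .87 to .93 at d = .25, detectable effect .226 to .205.

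**3. What the phrase means in its other use.** For n = 400, .62 at d = .25 gives λ = 1.960 + .305 = 2.265. At d = .30, λ = 2.265 × .30/.25 = 2.718, and power is Φ(.759) = .776. The 80% detectable effect is .25 × 2.802/2.265 = .309. There, 'optimally powered' at d = .30 does mean about .80.

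**4. Can the n = 400 pair show which N = 900 figure is wrong?** Use the step 1 formula with t on J − 1 df. The values of s and c, and the 30 clinicians in the last row, are assumptions and are not in the documents.

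| Assumed inputs | N = 900, d = .25 | N = 900, d = .20 | n = 400, d = .30 | n = 400, d = .25 |
|---|---|---|---|---|
| Plan | .80, if so read | .75 | .80, if so read | .62 |
| s = .02, c = 1, J = 22 | .90 | .74 | .78 | .63 |
| s = .092, c = .69, J = 22 | .80 | .61 | .78 | .62 |
| s = .069, c = .92; J = 22 for N = 900, J = 30 for n = 400 | .80 | .61 | .77 | .615 |

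The first set of assumptions misses only the d = .25 statement. The other two miss only the .75. The subsample figures therefore do not discriminate.

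**The case against.** The strongest defence is that the plan never prints .80 beside d = .25. If 'optimally powered' means only 'at least .80', then power of .91 at d = .25 and .75 at d = .20 are coherent and no printed number is false. This stands as a possible reading. It is the less natural one, because .80 is the paragraph's only target and the n = 400 pair uses the phrase for about .80. It also leaves d = .25 as something other than the 80% detectable effect, which is what a reader will take it to be.

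It is also fair to say that the consequence is limited. The plan presents the calculation as that of a preliminary pilot, and a null result would be read mainly from its confidence interval. That bears on how serious the point is, not on whether the paragraph is consistent.

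A reader might go further and infer that d = .25 is the wrong figure, so that the plan merely understates its power. A small effect variance of about .02 makes the other three figures fit, which is tempting. The documents do not support the inference. That variance is not stated, and equally unstated inputs (residual variance reduced to .69 by covariates, or more than 22 clinicians in the subsample, which 'at least 22' allows) make the .75 the only misfit. The two samples may also concern different outcomes, since the Ohio Scales are collected only in the subsample. One shared variance for both is an assumption.

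**Conclusion.** The point holds as an internal inconsistency, conditional on reading 'optimally powered' as about .80. On that reading one N = 900 statement is wrong: either power at d = .20 is .61 and not .75, or power at d = .25 is .91 and the 80% detectable effect is about .21 and not .25. This rests only on one common design and standard error for the two statements, and it holds for one- or two-sided alpha.

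Which figure is wrong cannot be determined from the documents, because the Optimal Design module, the effect variance across clinicians, any covariate adjustment and the sidedness are not given. Nor do the figures show that the trial is too small: on one branch the stated detectable effect is conservative, and on the other power at d = .20 is overstated by 14 points. The paragraph should be corrected, but the design is not in question on this ground.

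**What to change.** Rerun the calculation for clients randomised 1:1 within clinicians, then revise the paragraph as follows.

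- Replace 'optimally powered' with the numerical power at d = .25 and d = .20 (N = 900) and at d = .30 and d = .25 (n = 400).
- Restate the 80% detectable effect so that it agrees with those powers.
- Name the Optimal Design module, the effect variance across clinicians, any covariate adjustment, the number of clinicians assumed for each sample, and the sidedness of the test. Print the target as power = .80 and not β = .80.
- If the rerun reproduces .75 at d = .20, state power of about .91 at d = .25 and a detectable effect of about d = .21.
- If it reproduces .80 at d = .25, replace the .75 with about .61.
- If it reproduces neither, print the rerun values.

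The cost is one software run and one paragraph. Sample size, endpoints and analyses do not change.

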Youth and their caregivers will be included in Aims 2 and 3 in three ways. First, the four study clinics will be using the measurement-based care system with all clients receiving in outpatient and intensive outpatient mental health services (up to 2000 youth falling in the target age range) and have agreed to incorporate the study randomization scheme as a quality improvement effort. PI [name] has successfully used this approach in two previous randomized controlled trials of MBC^{46,47}. Second, in the session where the youth and caregivers complete the MBC measures through the Mirah platform, they will be recruited via the Mirah Platform to complete additional measures using the same procedures described for the Study 1 pilot trial. Recruitment will take the form of presenting a recruitment screen, followed by the consent form if they indicate they are interested in learning more about the study at the end of their measures; families will also be notified that this will be happening via a flyer that the clinic will be using to tell them about the Mirah system. These flyers are tailored for each office, but we have uploaded one as an example (Mirah PACE flyer- Nashville). We have also uploaded a copy of the recruitment screen (Recruitment Information for Research Subsample). The clinics may use Mirah at the clinic intake session, before the decision has been made which services the youth will receive. If a family consents to be in the research sample and then the youth does not go on to be assigned to one on the services using Mirah, they will be contacted and informed that they will no longer be eligible to take part in the study. Up to 400 youth and their caregivers will be enrolled in these additional research activities. Finally, for the final phase of the mixed-method study of implementation factors, a subset of up to 12 families who agreed to take part in the research study, stratified by their level of adherence to the MBC system, will be recruited with the assistance of their clinicians, who will provide them with a flyer describing the study (uploaded as PACE Family Triad Interview Recruitment Flyer) and asked if they would be interested in being contacted by research staff to hear about an opportunity to participate in qualitative interviews to better understand their experiences using the system. Families will be paid up to \$60 in gift cards (\$30 per informant) for participating in those interviews.

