Aim 2b will investigate potential factors associated with condition, client, or clinician that could influence a future SMART. GLMM (MLM with a logistic linking function) will be used to investigate factors associated with treatment and attrition from the study. In addition, differences between the full RCT sample (N = 900) and the Research Subsample (N = 400) will be examined utilizing data from electronic health records (EHR) to determine whether enrollment in the Research Subsample, and completing all 12 weeks, is associated with any demographic or clinical factors. We will also examine enrollment and attrition rates for clients within clinicians to determine whether any clinician factors might be associated with client-level participation in the study, along with comparing enrollment rates across clinics. As above, these analyses will inform design of the R01 SMART, including power analyses that take into account rates of NOT/OT and projected attrition.

MLM will also be used to compare the effects of study condition on SFSS change trajectories, Ohio Scores, and MBC mechanisms (**Aim 2c**). We will examine differences in MBC outcomes by feedback condition, nesting within treating clinician and controlling for clinic. If sample sizes in the research subsample prove too small for this analytic approach, analyses of variance will be used to test a time by treatment interaction. As a first step in comparing conditions on MBC mechanisms, we will aggregate the scores across sessions (within therapist) by averaging them or summing count variables (e.g., matches between a client being identified as NOT and the therapist recognizing deterioration) to create composite variables for each mechanism domain in Figure 2.

Finally, we will extend the MLMs tested to accommodate potential mediators and moderation by NOT status, diagnosis, and treatment type (**Aim 2d**). Mediation will be tested using the products of coefficients method¹²⁹, using bootstrapping to adjust for nonnormal, asymmetric confidence intervals¹³⁰. Algorithms for testing mediation using these methods are available in the package RMediation¹³¹ available in the software platform R. Moderation by NOT status will be tested by entering NOT status, along with the feedback condition by NOT

status interaction and other model covariates. Similar models will examine moderation by diagnosis and treatment type.

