Clients and Caregivers in the Research Subsample. At least 420 clients and caregivers will complete additional research measures via the Mirah system during the Aim 1c pre-pilot and the Aim 2 trial. Consent procedures will differ slightly for the two phases of the study. For the pre-pilot, caregivers will view a consent form and youth an assent form the first time they complete these measures in the Mirah system. If they have questions before participating, they will have the option to provide a phone number and ask for a call from study staff before deciding. For the Aim 2 Research Subsample, which involves a much larger sample of youth being recruited when they start treatment, youth and caregivers will view recruitment information when they complete their clinic intake questionnaires via Mirah. If they click that they are interested in the study, they will proceed to a screen with the consent/assent document. After reading the document, they will indicate yes, no, or "I have questions." If they have questions, they will next proceed to a Frequently Asked Questions (Research Subsample Frequently Asked Questions Page, uploaded in consent materials) page to see if their question is there. If not, they will be provided with the project phone number to call to ask questions. If they indicate at the intake that they have questions and do not consent, the study recruitment and consent/assent information will be presented one more time prior to their completion of the Mirah measures for their first session. If they do not agree to be in the study at that point, they will no longer be eligible to be part of the research subsample. Because youth and caregivers receive different links to complete their Mirah questionnaires, they will be asked to assent and consent separately, and it is possible that youth may consent prior to their caregivers consenting. However, neither youth nor caregivers will complete research measures unless both have consented/assented. We are requesting a waiver of signed consent for both the pre-pilot and research subsample subsample participants. For the pre-pilot obtaining written consent would increase the study risk by providing identifying information to the study team. For the research subsample, the research

team will obtain identifying information from participants in order to give them gift cards, but the study is online, so it is not feasible to get signed consent and the study is minimal risk.

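### The Research Subsample power (.62 at d = .25) counts all 400 enrolled youth as giving outcome data and makes no allowance for attrition

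*Combined protocol and SAP*

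**What the plan says.** Section 12 (Sample size and power calculations) introduces the subsample comparison with "With respect to power assessing differences by feedback condition in the Research Subsample (n = at least 22 clinicians and 400 adolescents". It says that the comparison "will be optimally powered for a small-moderate effect of $d = .30" and then: "Assuming an effect size of $d = .25$ yields power of .62". The paragraph does not mention attrition, retention or inflation of the sample.

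The same number appears as the enrolment figure in sections 3, 7, 10 and 12, but not always in the same sense. Section 7 words it as a maximum: "Up to 400 youth and their caregivers will be enrolled in these additional research activities". Section 30 words it as a minimum: "At least 420 clients and caregivers will complete additional research measures via the Mirah system". That count includes the pre-pilot, which section 7 limits to 20 dyads, so it implies 400 or more in the trial. In section 12 it is unclear whether the words for a minimum cover only the clinicians or the adolescents too.

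The plan foresees loss in several places:

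- Section 12, Aim 2b, models attrition and treats completion of all 12 weeks as something that varies between youth. It reserves "power analyses that take into account rates of NOT/OT and projected attrition" for the later R01 trial.
- Section 7 says of consented youth who are not then placed in a service using Mirah that "they will be contacted and informed that they will no longer be eligible to take part in the study".
- Section 14 withdraws youth who leave clinic care or can no longer complete assessments. Those who stop treatment voluntarily may still be approached for the 6- and 12-week assessments.
- Section 10 collects the Ohio Scales and the longer mechanism measures at enrolment, 6 and 12 weeks, through REDCap links e-mailed to families.

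**The concern.** If 400 is the number enrolled, it is not the number with a follow-up Ohio score unless nobody is lost. A youth with only the enrolment wave adds nothing direct to a contrast of change. Stated power that assumes complete data is too high on its own inputs as soon as some youth are lost.

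Section 9 names the youth- and caregiver-reported Ohio scales as primary endpoints, available in this subsample only. A null Ohio result would be judged against .62 when the power under the same model might be closer to one half. The plan also expects an overall effect below the .31 seen in a not-on-track subgroup. Under the model below, the effect detectable at .80 power is already about .31 with complete data, so any loss pushes it above that value.

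**Working it through.** **Inputs from the documents.** N = 400 and J = 22 clinicians (section 12, power paragraph); 1:1 randomisation of clients (section 10); p = .05, taken as two-sided; target power .80 (printed as a value of beta); software Optimal Design 3.1.

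**Inputs assumed.** The design module and the effect-size variance are not given. I take clients randomised within clinicians (multisite design), an effect-size variance of s² = .02, and no outcome variance explained by covariates. The .02 is fitted: it was chosen because it comes close to the printed figures.

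**Formula.** With n = N/J clients per clinician, the noncentrality is λ = J·d² / (s² + 4/n) = 22·d² / (.02 + 88/N). Power is the probability that a noncentral F(1, 21; λ) exceeds the .05 critical value, 4.325.

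**Reproducing the plan.**

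- N = 400, d = .25: λ = 22 × .0625 / (.02 + .22) = 1.375 / .24 = 5.73; power .627 (stated .62).
- N = 400, d = .30: λ = 1.98 / .24 = 8.25; power .782 (target .80).
- N = 900, d = .20: λ = .88 / .1178 = 7.47; power .741 (stated approximately .75).
- N = 900, d = .25: power .903, where the plan claims only its target of .80. The model does not match this figure, so it is a plausible guess at the sponsor's inputs and no more.

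The first three agree within about two points, and each uses the full 400 or 900 with no loss.

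**Applying a loss.** The documents give no rate, so 10 to 30% is an assumed range.

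| Assumed loss | Youth analysed | Power, d = .25 | Power, d = .30 | Effect detectable at .80 power |
|---|---|---|---|---|
| 0% | 400 | .627 | .782 | .307 |
| 10% | 360 | .585 | .742 | .322 |
| 20% | 320 | .540 | .695 | .340 |
| 30% | 280 | .490 | .641 | .362 |

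**Sensitivity to the fitted variance.** At d = .25, going from 400 to 320 youth changes power from .664 to .569 with s² = 0, from .645 to .554 with .01, and from .609 to .526 with .03. The drop is 8 to 10 points throughout, so the size of the loss depends little on the fitted value.

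**Possible offsets, same model.**

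- More clinicians: 50 clinicians with 360 youth gives .627 / .783 (d = .25 / .30), which cancels a 10% loss. At 20% loss, 50 clinicians give .578 / .735 and 200 give .601 / .758, still short of .62 / .80.
- Covariate gain: if baseline or repeated measures explain a share R² of outcome variance, 4/n becomes 4(1 − R²)/n. An assumed R² of .10 with 360 youth, or .20 with 320, returns exactly the full-data values of .627 / .782. An assumed R² of .25 with 280 gives .600 / .756.

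**The case against.** The strongest reply is that the printed figure need not be optimistic. The planned multilevel models use partial follow-up, so a youth with week 6 but not week 12 still contributes. The power paragraph credits nothing to baseline or repeated measures, and a modest R² would cancel a 10 to 20% loss. Section 12 gives 22 clinicians as a minimum and section 7 allows up to 200. Mechanism data also come from an item at up to 12 routine Mirah sessions, so a missed REDCap wave does not lose all of them. The study calls itself preliminary and openly reports .62, and Aim 2b promises that R01 planning will allow for attrition.

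Most of this stands, and it rules out two stronger readings that a reader might infer. One is that 400 is a hard enrolment ceiling: section 7 says so, but section 30 implies a floor, and section 7 does not say whether youth made ineligible after consent are replaced. The other is that .62 is a best case that the trial cannot reach: no retention rate is given, and the offsets could restore it.

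What the reply does not do is justify the printed number. The power paragraph claims no covariate gain, and extra clinicians alone do not recover a 20% loss. The fallback in section 12, analysis of variance if the subsample proves too small, would in its conventional repeated-measures form drop incomplete cases just when loss is greatest.

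**Conclusion.** The point holds as an unstated assumption. It is not an arithmetic error: .62 reproduces closely with complete data. The subsample power treats enrolment as data in hand, makes no allowance for the attrition and withdrawal that the plan itself foresees, and enrolment is not raised above 400 to compensate.

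Other inputs unchanged, an assumed 10 to 30% loss costs roughly 4 to 14 points of power at either effect size. These figures rest on the assumed retention range, the multisite model with 22 clinicians, the fitted variance of about .02 and no covariate gain; they are illustrative, and the offsets could remove part or all of the shortfall. The Ohio scales, collected only at the e-mailed waves, are the most exposed; the session-level mechanism items are less so. The comparison of 900 youth on the SFSS is a separate calculation, outside this point.

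**What to change.** In section 12, restate the subsample power for the number of youth expected to give at least one follow-up Ohio assessment, over a stated retention range. State the effect-size variance used and any baseline R² credited, so that a gain from adjustment is set openly against the loss.

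Reconcile sections 7, 12 and 30 on whether 400 is a target, a minimum or a maximum for the Aim 2 trial, and say whether youth found ineligible after consent count towards it or are replaced.

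This is a text change with no effect on enrolment. Its cost is a somewhat less favourable stated power, unless a supported R² makes up the difference.
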